8.3.1. Time Period and Frequency for Collecting AE and SAE Information

- All SAEs will be collected from the start of treatment until the follow-up visit at the time points specified in the SoA (Section 1.3).
- Medical occurrences after obtaining informed consent but before the initiation of study treatment will be recorded on the Medical History/Current Medical Conditions section of the case report form (CRF) not the AE section.
- All SAEs will be recorded and reported to the sponsor or designee immediately and under no circumstance should this exceed 24 hours of occurrence of SAE, as indicated in [Appendix 3](#). The investigator will submit any follow up information to the sponsor within 24 hours of occurrence.
- Investigators are not obligated to actively seek AEs or SAEs after the conclusion of the study participation. However, if the investigator learns of any SAE, including a death, at any time after a participant has been discharged from the study, and he/she considers the event to be reasonably related to the study treatment or study participation, the investigator must promptly notify the sponsor.

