5.2. Exclusion Criteria

Participants are excluded from the study if any of the following criteria apply:

Medical Conditions

1. Known history of hypersensitivity to Griseofulvin.
2. Participants who have taken prescription medications or over-the-counter products (including vitamins, minerals and/or herbal supplements) within 14 days prior to administration of IMP.
3. Any medical or surgical conditions, which might significantly interfere with the functioning of gastrointestinal tract, blood-forming organs etc.

4. History of cardiovascular, renal, hepatic, ophthalmic, pulmonary, neurological, metabolic, haematological, gastrointestinal, endocrine, immunological or psychiatric diseases.
5. History of malignancy (including skin cancers) or other serious diseases.
6. History of porphyria.
7. Known history of SLE (Systemic lupus erythematosus) in the exclusion criteria.

Prior/Concomitant Therapy

8. Participants consuming aspirin, oral contraceptive pills, phenobarbital, and warfarin having potential to trigger drug interactions with griseofulvin for any ailment in the previous 28 days, prior to dosing day.

Prior/Concurrent Clinical Study Experience

9. Participation in a clinical drug study or bioequivalence study 90 days prior to period I dosing of the present study.

Diagnostic assessments

10. Participants with positive HIV tests, HBsAg or Hepatitis-C tests.
11. Found positive in breath alcohol test.
12. Found positive in urine test for drug abuse.

Other Exclusions

13. Blood donation 90 days prior to period I dosing of the present study.
14. History of problem in swallowing pills.
15. Any contraindication to blood sampling i.e. keloid formation.
16. Sensitivity to heparin or heparin-induced thrombocytopenia.
17. Premenarchal female subjects

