5.4. Screen Failures

Screen failures are defined as participants who consent to participate in the clinical study but are not subsequently randomized in the study. A minimal set of screen failure information is required to ensure transparent reporting of screen failure participants to meet the Consolidated Standards of Reporting Trials (CONSORT) publishing requirements and to respond to queries from regulatory authorities. Minimal information includes demography, screen failure details, eligibility criteria, any protocol deviations and any serious adverse events (SAEs).

Individuals who do not meet the criteria for participation in this study (screen failure) may not be rescreened.

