8.5. Pharmacokinetics

Whole blood samples of approximately 5 mL will be collected for measurement of plasma concentrations of Griseofulvin as specified in the SoA.

An intravenous cannula will be inserted into the participant's arm for the collection of the blood samples before the pre-dose blood sample and up to 24.00 hrs post-dose. If difficulties occur in blood withdrawal or if the participant is not feeling comfortable with the cannula, then the cannula will be removed before 24.00 hrs post-dose and the remaining blood samples will be collected through fresh vein puncture or by recannulation. When meals, vitals and sample collections coincide, samples will be collected first followed by vitals and then meal will be served.

Before every blood sample collection, 0.2 mL of blood present in the intravenous cannula will be discarded during the use of the intravenous cannula except for the ambulatory sample. Also after every blood sample collection, 0.2 mL of heparinised saline (by mixing 1 mL of 5000 IU/5mL of heparin with 500 mL of normal saline) will be injected into the intravenous cannula.

Twenty-Two (22) blood samples will be collected in Na-Heparin vacutainers at pre-dose (collected within 01.00 hour prior to dosing), 00.50, 01.00, 01.50, 02.00, 02.50, 03.00, 03.50, 04.00, 04.50, 05.00, 05.50, 06.00, 06.50, 07.00, 08.00, 10.00, 12.00, 24.00, 48.00, 72.00 and 96.00 hours post dose.

Note: The actual time of blood collection (24 hour clock) will be considered for calculation of PK parameters. Duration of 2 minutes is required for the completion of procedure of blood sample collection. Hence, the reason for deviation up to 2 minutes for the blood sample collection activity need not be documented. However, the reason for delay beyond 2 minutes will be documented in the case record form and/or other document.

Blood samples after 24 hrs will be collected on ambulatory basis through direct vein puncture. The actual end-point time of collection of each blood sample will be recorded in the CRF.

Ambulatory blood sample will be collected up to 04.00 hrs from the scheduled time of blood sample collection. If the participant reports for blood sample collection beyond 04.00 hrs, the blood sample will not be collected, and the participant will be requested to come for the next ambulatory sample (if any).

Approximate blood loss during the study:

		Males	Females
Total PK blood samples (66 x 5 mL)	:	330 mL	330 mL
Pre study screening	:	Upto 10 mL	Upto10 mL

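### SAE collection opens at first dosing (Section 8.3.1, Appendix 3), so a serious procedure-related event before dose 1 triggers no 24-hour SAE report, in conflict with Sections 4.1, 5.4 and 8.2

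*Protocol*

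**What the plan says.** Protocol Section 8.3.1 sets the window: "All SAEs will be collected from the start of treatment until the follow-up visit at the time points specified in the SoA". Its next bullet deals with everything before that: "Medical occurrences after obtaining informed consent but before the initiation of study treatment will be recorded on the Medical History/Current Medical Conditions section". The same bullet keeps such events out of the CRF's adverse-event pages. Neither bullet makes an exception for an event that is serious or that a study procedure caused. The expedited duty in the same section applies to SAEs only: "All SAEs will be recorded and reported to the sponsor or designee immediately", with a 24-hour limit. The section mentions harm related to study participation once, for SAEs that the investigator learns of after the participant has been discharged.

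Appendix 3 supplies the definitions. Section 10.3.1 makes an AE an untoward occurrence linked in time to use of a study treatment. Section 10.3.2 adds that an event which is not an AE cannot be an SAE, however serious it is.

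Other sections point the other way:

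- Section 5.4, on people who consent but are not randomized: "Minimal information includes demography, screen failure details, eligibility criteria, any protocol deviations and any serious adverse events (SAEs".
- Section 8.2 has participants monitored for AEs and SAEs over the whole study.
- Section 4.1 has adverse-reaction information collected and recorded at admission on Day -1, before any dose.
- Section 8.3 makes the investigator responsible for following AEs related to the treatment or to the study.

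**The concern.** Study procedures start before the first tablet is taken. Blood is drawn at screening and before check-in, and Section 8.5 states: "An intravenous cannula will be inserted into the participant's arm for the collection of the blood samples before the pre-dose blood sample". Each cannula sample is followed by an injection of heparinised saline. The protocol itself recognises a risk here, because "Sensitivity to heparin or heparin-induced thrombocytopenia" is a listed exclusion.

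If one of these procedures causes a serious event before dose 1, the site has conflicting instructions. Section 8.3.1 and Appendix 3 make it medical history; Sections 5.4, 8.2 and 4.1 treat safety events as collectable before dosing. The site would have to choose between them under a 24-hour clock. If it follows Section 8.3.1, nothing starts that clock for the sponsor, the health authority or the ethics committee.

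**Working it through.** No figure in the plan needs to be reproduced. The check sets the passages side by side and follows one event through them.

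**1. What starts the 24-hour clock.** The duties in Section 8.3.1, Section 8.3.4 and Table 2 of Section 10.3.4 are all triggered by an SAE. An event that is not classed as an SAE starts none of them.

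**2. Whether a pre-dose event can be an SAE.** Under Section 8.3.1 it falls before the collection window and goes to Medical History. Under Section 10.3.1 it is not linked to use of a study treatment, so it is not an AE. Under Section 10.3.2 it therefore cannot be an SAE. Timing and definition close the route separately.

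**3. Whether the cannula and flush come before dose 1.** The blood-loss table in Section 8.5 counts 57 discards of cannula blood over three periods: 57 / 3 = 19 per period. There are 22 samples per period, of which 3 (48, 72 and 96 hours) are ambulatory and taken by direct puncture: 22 - 3 = 19. The 19 cannula samples therefore include the pre-dose one. The order on Day 1 is cannula, discard, pre-dose sample, flush, dose.

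**4. The same serious cannulation or flush event in different people.**

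| Situation | Section 8.3.1 and Appendix 3 | Other provision | Result |
|---|---|---|---|
| Consented, not randomized | Medical history, not an SAE | Section 5.4 requires any SAE | Direct conflict |
| Randomized, event before dose 1, never dosed | Medical history, not an SAE | Not a screen failure; outside the Safety Analysis Set (Section 9.3) | No SAE route |
| Randomized, event before dose 1, dosed later | Medical history, not an SAE | In the Safety Analysis Set, but the event is not an AE | No SAE route |
| Same event before dosing in Period 2 or 3 | Window already open | 24-hour rule applies | Reported as an SAE |

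The last two rows show that one procedure-related harm changes class according to the period in which it happens.

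**5. Size.** At most 36 participants are randomized, giving at most 36 x 3 = 108 dosing admissions. Of these, 36 / 108 = one third (the first-period ones) have their pre-dose procedures before the window opens. Screening may be up to 21 days before the first dose, and the last 10.5 hours or more are spent in house. The documents give no event rate for these procedures.

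**The case against.** The case for leaving the text alone has several parts.

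*The event would still be seen.* It is written in the CRF. Section 8 asks that immediate safety concerns be discussed with the sponsor at once. Section 10.1.1 has the investigator notify the ethics committee of SAEs or other significant safety findings, as that committee's procedures require. Section 8.2 has the reason for not completing stated in the CRF and the clinical report, and SAP Section 10.8.4 lists discontinued subjects. This stands. A reader might infer that serious procedural harm would go unreported; the documents do not support that. What is missing is the defined 24-hour SAE report, which the general clauses do not replace.

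*Screen failures are covered.* Section 5.4 does ask for their SAEs, and other participants' pre-dose events are recorded as medical history. A reader might therefore call the screening weeks unmonitored, and that too would be wrong. For screen failures the fault is a contradiction; the gap in the route concerns randomized participants before dose 1.

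*A false baseline would not hide a recurrence.* A reader might fear that a pre-dose reaction entered as history would mask a later one. Section 10.3.1 counts an increase in frequency or intensity of a pre-existing condition as an AE and excludes only fluctuations that do not worsen. That largely answers the fear.

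*The Schedule of Activities may already start earlier.* In the extracted tables the AE and SAE lines appear to begin at the Day -1 check-in. The position of a line in extracted text is not reliable, so I do not rely on it either way.

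*The risk is small.* By the recipe in Section 8.5, 1 mL of 5000 IU/5 mL is 1000 IU. In 500 mL that is about 2 IU/mL, or about 0.4 IU per 0.2 mL flush, and known heparin sensitivity is excluded. This limits the expected count. It does not tell the site what to do when an event happens.

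*Starting at first dose is a legitimate choice.* It may be, but Sections 4.1, 5.4 and 8.2 do not follow that choice, so the protocol cannot be applied consistently as written.

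**Conclusion.** The point holds as a conflict between stated rules that leaves a narrow gap in expedited reporting. A serious event caused by a study procedure between consent and dose 1 has no 24-hour SAE route in a randomized participant. If that person is never dosed, they are also outside the Safety Analysis Set. For screen failures, Section 5.4 contradicts Section 8.3.1 and Appendix 3.

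Expected events are few. The bioequivalence and dose-proportionality conclusions are unaffected, because no pharmacokinetic endpoint or analysis set depends on this rule. The change is worth making because it protects participants at little cost.

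Two assumptions matter. First, Section 10.3.1 is read so that an event before any dose is not linked to use of a study treatment. A looser reading would soften the definitional bar but not the window in Section 8.3.1. Second, treatment sequence is assigned before the Day 1 cannula is placed. The Schedule of Activities as extracted has no randomization row; if assignment came later, the person would be a screen failure and the conflict with Section 5.4 would apply instead.

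**What to change.** - **Section 8.3.1, SAE bullet:** record and report SAEs related to study participation (protocol-required procedures such as blood sampling, cannulation and the heparinised flush) from signing of consent, and other SAEs from the start of treatment.
- **Section 8.3.1, Medical History bullet:** limit it to pre-dose events that are not such SAEs.
- **Appendix 3, Sections 10.3.1 and 10.3.2:** add the same exception to the AE and SAE definitions. Without this, the amended Section 8.3.1 would be defeated by the rule that a non-AE cannot be an SAE.
- **Sections 4.1, 5.4, 8.2 and the Schedule of Activities (also reproduced in SAP Appendix 1):** reconcile them with the new start point, including whether the SAEs required by Section 5.4 are limited to participation-related ones.

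The Safety Analysis Set need not change, since it serves the objective on safety of a single dose.

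The cost is a few sentences in the protocol and matching edits to the schedule, with an occasional extra SAE report from the pre-dose period. Sample size, models and acceptance limits stay as they are.

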8.3.2. Method of Detecting AEs and SAEs

- The method of recording, evaluating, and assessing causality of AEs and SAEs and the procedures for completing and transmitting SAE reports are provided in [Appendix 3](#).
- Care will be taken not to introduce bias when detecting AE and/or SAE. Open-ended and non-leading verbal questioning of the participant is the preferred method to inquire about AE occurrence.

8.3.3. Follow-up of AEs and SAEs

After the initial AE/SAE report, the investigator is required to proactively follow up with each participant at subsequent visits/contacts. All SAEs will be followed up until the event is resolved, stabilized, otherwise explained, or the participant is lost to follow-up (as defined in Section 7.3). Further information on follow-up procedures is given in [Appendix 3](#).

8.3.4. Regulatory Reporting Requirements for SAEs

- Within 24 hours of SAE occurrence (both Initial and Follow up information), the Investigator should complete a soft copy of the Table 5 format of the New Drugs & Clinical Trial Rules, 2019 with details of the SAE (as required by the HA) and Forward the completed Table 5 scan copy to the Sponsor, HA and Ethics Committee.
- Within 14 calendar days of SAE occurrence, the Investigator should provide causality assessment to the HA, Ethics Committee and Head of Institution.

- Within 14 calendar days of Sponsor (GSK) awareness of SAE, the Sponsor forwards the Sponsor causality via completed Final Table 5 to the Chairman of Ethics Committee, Head of Institution and to the HA (along with other relevant documents related to submission to the HA).

8.3.5. Pregnancy

- Details of all pregnancies in female participants and, female partners of male participants will be collected after the start of study treatment and until 6 months after the last dose.
- If a pregnancy is reported, the investigator should inform GSK within 24 hours of learning of the pregnancy and should follow the procedures outlined in [Appendix 4](#).
- Abnormal pregnancy outcomes (e.g., spontaneous abortion, fetal death, stillbirth, congenital anomalies, ectopic pregnancy) are considered SAEs and should be reported within 24 hours of occurrence (please see details provided in [Appendix 3](#)).

8.4. Treatment of Overdose

For this study, any dose of Griseofulvin Tablets > 500 mg, within a 24-hour time period will be considered an overdose.

GSK does not recommend specific treatment for an overdose. A detailed description of overdose of Griseofulvin Tablets is provided in the Summary of Product Characteristics ⁽⁶⁾.

In the event of an overdose, the investigator should:

1. Contact the Medical Monitor immediately.
2. Closely monitor the participant for AE/SAE and laboratory abnormalities until Griseofulvin can no longer be detected systemically (at least 5 days).
3. Obtain a plasma sample for PK analysis within 5 days from the date of the last dose of study treatment if requested by the Medical Monitor (determined on a case-by-case basis).
4. Document the quantity of the excess dose as well as the duration of the overdosing in the CRF.

Decisions regarding dose interruptions or modifications will be made by the investigator in consultation with the Medical Monitor based on the clinical evaluation of the participant.

8.5. Pharmacokinetics

Whole blood samples of approximately 5 mL will be collected for measurement of plasma concentrations of Griseofulvin as specified in the SoA.

An intravenous cannula will be inserted into the participant's arm for the collection of the blood samples before the pre-dose blood sample and up to 24.00 hrs post-dose. If difficulties occur in blood withdrawal or if the participant is not feeling comfortable with the cannula, then the cannula will be removed before 24.00 hrs post-dose and the remaining blood samples will be collected through fresh vein puncture or by recannulation. When meals, vitals and sample collections coincide, samples will be collected first followed by vitals and then meal will be served.

Before every blood sample collection, 0.2 mL of blood present in the intravenous cannula will be discarded during the use of the intravenous cannula except for the ambulatory sample. Also after every blood sample collection, 0.2 mL of heparinised saline (by mixing 1 mL of 5000 IU/5mL of heparin with 500 mL of normal saline) will be injected into the intravenous cannula.

Twenty-Two (22) blood samples will be collected in Na-Heparin vacutainers at pre-dose (collected within 01.00 hour prior to dosing), 00.50, 01.00, 01.50, 02.00, 02.50, 03.00, 03.50, 04.00, 04.50, 05.00, 05.50, 06.00, 06.50, 07.00, 08.00, 10.00, 12.00, 24.00, 48.00, 72.00 and 96.00 hours post dose.

Note: The actual time of blood collection (24 hour clock) will be considered for calculation of PK parameters. Duration of 2 minutes is required for the completion of procedure of blood sample collection. Hence, the reason for deviation up to 2 minutes for the blood sample collection activity need not be documented. However, the reason for delay beyond 2 minutes will be documented in the case record form and/or other document.

Blood samples after 24 hrs will be collected on ambulatory basis through direct vein puncture. The actual end-point time of collection of each blood sample will be recorded in the CRF.

Ambulatory blood sample will be collected up to 04.00 hrs from the scheduled time of blood sample collection. If the participant reports for blood sample collection beyond 04.00 hrs, the blood sample will not be collected, and the participant will be requested to come for the next ambulatory sample (if any).

Approximate blood loss during the study:

		Males	Females
Total PK blood samples (66 x 5 mL)	:	330 mL	330 mL
Pre study screening	:	Upto 10 mL	Upto10 mL
Post study evaluation	:	Upto 10 mL	Upto 10 mL
Discarded heparinised blood (57 x 0.2 mL)	:	11.4 mL	11.4 mL
*For ALT test (before check-in for each	:	6 mL	6 mL

study period)			
Serum β -hCG (3 x 2 mL)	:	-	6 mL
Approximate blood loss	:	367.4 mL	371.4 mL

*Samples for ALT will be collected in PlainTube/ Plain Gel Tube

Blood withdrawal beyond this specified blood volume in the study will be considered as an incidental blood loss.

The incidental blood loss may occur due to following reasons.

1. For performing pending laboratory tests if study participant are primarily screened for other study not having such investigations.
2. For performing pending laboratory tests on the day of check-in for period I if such investigations are not performed on the day of screening due to any reason.
3. For repeating PK sample due to any reason after check-in in the study if required in the opinion of the investigator (example: loss of blood sample due to spillage or breaking of sample container etc).

It is expected that incidental blood loss due to above mentioned reasons will not exceed a blood loss up to 20 ml.

The participants will be compensated as per the compensation policy of CRO.

If additional blood sample is taken for safety evaluation anytime after check in for first period, no compensation will be provided for such blood loss.

Instructions for the collection and handling of biological samples will be specified in the SRM. The actual date and time (24-hour clock time) of each sample will be recorded.

Samples will be used to evaluate the PK of Griseofulvin. Each plasma sample will be divided into 2 aliquots (1 each for PK and a back-up). Samples collected for analyses of Griseofulvin plasma concentration may also be used to evaluate safety aspects related to concerns arising during or after the study.

Name and address details of Bio-Analytical Investigator:

Set# 01 (PK aliquot) will be shipped to:

Name: [name] [REDACTED], Ph.D. (Analytical Chemistry)

Address: Analytical Facility:

Accutest Research Laboratories (I) Pvt. Ltd.,

[name],

Maharashtra, INDIA.

Tel: PPD [REDACTED]

Fax: [REDACTED]

Email : PPD [REDACTED]

Set# 02 (back-up aliquot) will be forwarded to the same analytical laboratory only after confirmation of receipt of Set# 01 by the analytical laboratory, if necessary.

A validated LC-MS/MS analytical methodology will be used for the determination of Griseofulvin from the human plasma samples. Validation of the methodology will be carried out in accordance with applicable guidelines and the applicable SOP of analytical facility of Accutest Research Laboratories (I) Pvt. Ltd which are designed in accordance with the regulatory guidelines such as USFDA, EMEA, DCGI etc.

The following parameters (as applicable for BE demonstration and for dose proportionality) will be calculated for each participant-formulation combination using the non-compartmental model by using statistical package SAS[®] 9.2 or higher version:

All concentration values below the limit of quantification (BLQ) will be set to zero for the estimation of pharmacokinetic parameters.

If the pre-dose value is >5 percent of C_{max} , the respective period of that subject will be dropped from all PK evaluations and statistical evaluations

The pharmacokinetic samples of subjects dropped out or withdrawn due to vomiting / diarrhoea or any other reason will not be analyzed for the respective study period. The samples of subjects completing at least 2 periods of the study will be subjected to statistical analysis.

Depending upon availability of data, the subject will be either included in bioequivalence evaluation or dose proportionality evaluation.

Primary parameters

C_{max}	Maximum observed drug concentration during the study.
AUC_{0-t}	Area under the plasma concentration - time curve measured to the last quantifiable concentration, using the linear trapezoidal rule.
AUC_{0-inf}	AUC_{0-t} plus additional area extrapolated to infinity, calculated using the formula $AUC_{0-t} + C_t/K_{el}$, where C_t is the last measurable drug concentration and K_{el} is the elimination rate constant.

Secondary parameters

T_{max}	Time to observe maximum drug concentration. If the maximum value occurs at more than 1 time point, T_{max} is defined as the first time point with this value.
AUC_{0-t} / AUC_{0-inf}	Ratio of AUC_{0-t} and AUC_{0-inf}
Residual area	Extrapolated area $(AUC_{0-inf} - AUC_{0-t}) / AUC_{0-inf}$

K_{el}	Apparent first – order terminal elimination rate constant calculated from a semi-log plot of the plasma concentration versus time curve, using the method of least square regression.
$t_{1/2}$	Terminal half-life as determined by quotient $0.693/K_{el}$
Vd	Fluid volume that would require to contain the whole drug in the body at the same conc. found in the plasma is given by formula, $Dose / (K_{el} \times AUC_{0-inf})$
CL	Clearance of a given individual in the measure of his body capacity to eliminate a drug and is given by formula $Dose / AUC_{0-inf}$

The pharmacokinetic parameters will not be calculated in case of inconclusive concentration time profile (e.g. lack of sufficient measurable concentrations).

No value of K_{el} , Residual area, AUC_{0-t}/AUC_{0-inf} , AUC_{0-inf} , Vd, CL and $t_{1/2}$ will be reported for cases that do not exhibit a terminal log-linear phase in the concentration versus time profile.

Name and address details of Biostatistician (For PK analysis):

Name: [name], M.Sc. (Statistics)/ [name] (B. Com, SAS Programmer)

Address: Statistical Facility:

Accutest Research Laboratories (I) Pvt. Ltd.,
[name],
[name],
Maharashtra, INDIA.

Tel: PPD

Fax: PPD

Email:

PPD

All the procedures of PK analysis will be carried out in accordance with applicable guidelines and the applicable SOP of statistical facility of Accutest Research Laboratories (I) Pvt. Ltd.

